## 4.2.2 Adverse Events of Special Interest

As soon as possible (desired within 24 hours of Investigator or study coordinator awareness), the investigational center staff must report all AESIs (including DKA) to the Sponsor. For these events, the AE CRF will be completed with all known details as soon as possible, this will serve as notification to the Sponsor. If the study database cannot be accessed due to technical problems, contact the Sponsor and provide the known details of the event. Once the access issue has been corrected, the event should be entered onto an AE CRF.

Source documents that support the event (e.g., clinic notes, hospital admission and discharge records, lab reports, EMT reports, ER/Urgent Care) should be provided to the Sponsor. All source documents/medical records should be redacted. Each source page should be identified with the subject ID.

## 4.2.3 Serious Adverse Events

Prompt notification by the Investigator to the Sponsor of an SAE (within 24 hours) is essential so that legal obligations and ethical responsibilities toward the safety of participants and the safety of a study intervention under clinical investigation are met.

The Sponsor has a legal responsibility to notify both the local regulatory authority and other regulatory agencies about the safety of a study intervention under clinical investigation. The Sponsor will comply with all applicable regulatory requirements relating to safety reporting to the regulatory authority, institutional review board (IRB), and Investigators.

Any SAE brought to the attention of the Investigator at any time after the end of the study for the subject and considered by the Investigator to be caused by the investigational product with a reasonable possibility should also be reported.

## 4.2.4 Procedures for Documenting Pregnancy During Study

If a female subject becomes pregnant during the study, the Investigator will notify the medical monitor immediately following pregnancy confirmation. A subject who becomes pregnant over the course of this study will be discontinued from study drug and followed for safety outcomes until 30 days beyond resolution of the pregnancy. Pregnancy is not in and of itself an AE.

Confidential Page 60 of 70

mannkind

However, if any adverse findings in a child or fetus of a subject exposed to the study drug occur before conception or during pregnancy, these should be reported as AEs.

Confidential Page 61 of 70

#### 5 DATA MANAGEMENT AND STATISTICAL ANALYSIS

### 5.1 Data Management Considerations

Paper CRFs will be employed for this study. Completed CRFs for this study will be forwarded to the Sponsor or its representative where editing and construction of a validated database will occur. Data will be quality checked, double-entered, and verified before entry into the database. Queries will be issued for any inconsistencies, omissions, and discrepancies and will be resolved by the appropriate parties. The statistical analysis of these data will be performed by the Sponsor or its representative. All AEs will be coded using the latest version of the Medical Dictionary for Regulated Activities (MedDRA). Concomitant medications will be coded using the latest version of the WHO Drug Global Dictionary. Data management details will be outlined in a separate data management plan.

### 5.2 Statistical Considerations

Any deviations from the analyses described below will be documented prior to database lock, which will be described in the clinical study report.

#### 5.3 General Considerations

All statistical processing will be performed using the most current version of statistical software (such as MiniTab, MATLAB, or Microsoft Excel) at the time of the analysis. Summary tables (descriptive statistics and/or frequency tables) will be provided for screening and/or baseline variables, efficacy variables, and safety variables. Continuous variables will be described by descriptive statistics (n, mean, median, standard deviation, minimum, and maximum). Frequency counts and percentage of subjects within each category will be provided for categorical data.

Individual data will be listed and sorted by treatment, subject ID, visit, and time point.

Database lock will occur upon the completion of the study.

### 5.4 Primary Endpoint

This study will evaluate the efficacy and safety of Afrezza combined with basal insulin or AID with insulin pump therapy, based on the change in HbA1c from baseline to the end of study.

### 5.4.1 Safety Endpoints

- Event rates and incidence Level 1 (<70 mg/dL) and Level 2 (<54 mg/dL) hypoglycemic events as confirmed by SMBG
- Event rates and incidence of severe hypoglycemic events, defined as events requiring assistance of another person to actively administer carbohydrate, glucagon, or other resuscitative actions
- Incidence and severity of AEs: TEAEs, SAEs, AESIs, and device complaints
- Change in FEV1 from screening to end of study

Confidential Page 62 of 70

#### 5.5 Randomization

This study is an open-label, randomized, three-arm study. Subjects will be randomized 2:2:1 to the Afrezza + AID, Afrezza + Insulin Degludec, and AID Control groups.

The randomization will target for a minimum of 3 subjects each who use Medtronic 670G/770G and Tandem Control IQ AID in each of the Afrezza groups, and a minimum of 2 subjects each who use Medtronic 670G/770G and Tandem Control IQ AID in the AID Control group.

### 5.6 Sample Size Justification

The sample size (25 subjects completing the study) was not determined using statistical methods as there is no statistical significance that will be derived.

## 5.7 Analysis Populations

The following analysis populations will be used:

- **Intent-To-Treat (ITT) Population**, defined as all subjects assigned to study treatment. The ITT Population will be the primary efficacy population.
- Per-Protocol (PP) Population, defined as all ITT subjects who have no major protocol
  deviations that would have an impact on the primary endpoint assessment during the 90-day
  randomized treatment period.

#### **5.8** Protocol Deviations

Major protocol deviations (number and percentage of subjects) will be summarized for the ITT Population. All protocol deviations will be reviewed by clinical and statistical personnel to identify important deviations (those anticipated to have an impact on efficacy or safety findings) before the primary database lock.

### 5.9 Subject Disposition

Disposition of subjects will be summarized for ITT Population. Number and percentage of subjects completed or discontinued from the study will be summarized by visit and/or study period. Reasons for discontinuation will also be summarized.

### 5.10 Demographic and Baseline Characteristics

Demographic and baseline characteristics, including usual insulin doses, will be summarized descriptively for the ITT Population. Summary statistics will include frequency and percentage, means, SD, minimum, and maximum as appropriate.

### 5.11 Medical History

Medical history data will be collected at the Screening Visit. The number and percentage of subjects with each medical history preferred term and system organ class will be summarized for ITT Population.

Confidential Page 63 of 70

#### 5.12 Concomitant Medications

All nonstudy medications will be coded with the current version of the WHO Drug Global Dictionary. Concomitant medications refer to nonstudy medications that have been used on or after administering the first dose of study drug. Among the concomitant medications, new concomitant medications refer to medications that are started after administering the first dose of study drug.

The number and percentage of subjects administering concomitant medications and new concomitant medications will be summarized by Anatomic Therapeutic Chemical Classification System Level 4 category and preferred term for the ITT Population.

### 5.13 Treatment Exposure and Compliance

Descriptive statistics will be used to summarize subject dosing information including the basal, bolus, and total insulin doses by visit.

A by-subject listing of study drug administration will also be provided.

## 5.14 Descriptive Summary of Efficacy

HbA1c values will be summarized at baseline and end of study for the ITT Population. CGM values and metrics will be summarized by visit. A summary table with descriptive statistics (n, mean, median, standard deviation, minimum, and maximum). CGM data will also be presented graphically.

### 5.15 Descriptive Summary of Safety

The incidence of hypoglycemia (total, nocturnal, and severe) and percentage time below 70 mg/dL and below 54 mg/dL will be reported. Nocturnal is defined as midnight to 0600 and severe hypoglycemia is defined as an event requiring assistance of another person to actively administer carbohydrate, glucagon, or other resuscitative actions.

The number and percentage of subjects with treatment-emergent AEs will be tabulated by system organ class and preferred term by relationship to treatment and by severity.

A summary table by study visit with descriptive statistics for  $FEV_1$  at screening and end of study will be provided. The  $FEV_1$  data will also be presented graphically.

Confidential Page 64 of 70

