## 4.1.3 Adverse Events of Special Interest

An adverse event of special interest (AESI) is an AE (serious or nonserious) of scientific and medical concern, specific to the investigational medicinal product or program, for which ongoing monitoring and rapid communication by the Investigator to the Sponsor may be appropriate. Such events may require further investigation in order to characterize and understand them.

For AESIs, the Sponsor must be informed immediately (i.e., within 24 hours), per the SAE notification guidelines described in Section 4.2.3.

The following AEs are considered AESIs:

- Acute bronchospasm
- Clinically relevant decline in pulmonary function (>20% decline from baseline percent predicted FEV1 OR respiratory symptoms not associated with URI
- Hypersensitivity reactions, including anaphylaxis, which can occur with insulin products, including Afrezza
- DKA

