Protocol Title: ABC [Afrezza with Basal Combination]: A Phase 4 Study of Mealtime Control with Afrezza in Adult Subjects with Type 1 Diabetes Mellitus in Combination with an Automated Insulin Pump or Insulin Degludec

Brief Title: Afrezza With Basal Combination (ABC)

Protocol Number: MKC-TI-192

Clinical Phase: Phase 4

SAP Document Version: Version 1.0

SAP Note: Redacted sections describe Data Management procedures for the study. Only Statistical sections are presented.

Sponsor: MannKind Corporation, [name]

NCT Number: NCT05243628

Data Management & Statistical Analysis Plan

Protocol Title	ABC [Afrezza with Basal Combination]: A Phase 4 Study of Mealtime Control with AfreZZA in Adult Subjects with Type 1 Diabetes Mellitus in Combination with an Automated Insulin Pump or Insulin Degludec
Protocol Identifier	MKC-TI-192
Protocol Version	1.1
Sponsor/Local Sponsor	MannKind Corporation
Document Version	1.0

1. Version History

Version	Summary of Change(s)	Author
1.0	Initial Version	[name] & [name]

2. Purpose

The purpose of this Statistical Analysis Plan (SAP) is to detail procedures and methods for executing the evaluation of primary and secondary endpoints. The study is not powered for statistical analysis.

3. Scope

This DMP & SAP cover study-related tasks and deliverables for the above referenced study. It describes how data will be collected, processed, QC'ed, stored, and analyzed.

4. Definitions & Acronyms

The following table lists the study terms specific-to and only used in this document

Term	Definition
A1c / HbA1c	Hemoglobin HbA1c

AE	Adverse Event
AID	Automatic Insulin Delivery
CGM	Continuous Glucose Monitor/Monitoring
CRF	Case Report Form
CSR	Clinical Study Report
DM	Data Manager
DMP	Data Management Plan
RAA	Rapid-acting insulin analogue
SAE	Serious Adverse Event
SAP	Statistical Analysis Plan
SMBG	Self-monitoring of blood glucose
(e)TMF	(electronic) Trial Master File

[figure not shown]
5. Data Storage

Database	Database Owner	Description of Data Stored
[REDACTED]	[REDACTED]	[REDACTED]
[REDACTED]		[REDACTED]
[REDACTED]		[REDACTED]
[REDACTED]	[REDACTED]	[REDACTED]

6. Data Collection and Processing

[REDACTED]	[REDACTED]

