8.2.4 Descriptive Summary of Safety

The incidence (number of events) of hypoglycemia confirmed by SMBG (total and severe) and the percentage time (by CGM) with glucose below 70 mg/dL and below 54 mg/dL will be reported. Nocturnal is defined as midnight to 0600 and severe hypoglycemia is defined as an event requiring assistance of another person to actively administer carbohydrate, glucagon, or other resuscitative actions. The number and percentage of subjects with treatment-emergent AEs will be tabulated by system, organ class, and preferred term by relationship to treatment, and by severity.

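### Change in FEV1 is a named safety endpoint, but the planned tables give neither its within-subject distribution nor a count against the protocol's own >20% decline criterion

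*Protocol*

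**What the plan says.** Protocol 5.4.1 and the synopsis list among the safety endpoints "Change in FEV 1 from screening to end of study". Protocol 5.15 then describes the analysis: "A summary table by study visit with descriptive statistics for" FEV1 "at screening and end of study will be provided", and FEV1 "data will also be presented graphically". It does not mention change, and does not say whether the graph shows subjects or groups.

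Protocol 4.1.3 sets a subject-level criterion. Clinically relevant decline in pulmonary function is an AESI, defined as ">20% decline from baseline percent predicted" FEV1 or, alternatively, respiratory symptoms without an upper respiratory infection. AESI incidence is itself a safety endpoint in 5.4.1.

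SAP 8.2.4 follows the synopsis safety text on hypoglycemia, CGM time below range and treatment-emergent AEs, which "will be tabulated by system, organ class, and preferred term by relationship to treatment, and by severity". It stops there: the FEV1 paragraph is absent, and no presented SAP section mentions FEV1, pulmonary function or AESIs. Redaction does not explain this, because the cover note states: "Redacted sections describe Data Management procedures for the study. Only Statistical sections are presented".

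Table 3 schedules FEV1 at V1, V14 and early termination (ET) only. Section 3.9.2.5 adds tests for subjects with symptoms, at the investigator's discretion.

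**The concern.** The test product is inhaled, and Protocol 1.3.1 lists bronchospasm in subjects with underlying chronic obstructive lung disease as an identified risk. Lung function is therefore a safety measure on which the report should be explicit. Because spirometry is scheduled only at the start and end, a fall without symptoms can be seen only by comparing a subject's two values. The endpoint is defined that way, but the stated table is not: it describes each visit separately. No section of either document asks anyone to compute the >20% criterion from the spirometry data. The risk is a report whose FEV1 table looks flat while a subject meets the protocol's own definition of relevant decline.

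**Working it through.** The documents give no power, SD or effect size for FEV1, so there is no planned figure to reproduce. The check is first of what the stated table can contain, and then of how visible one faller would be in it.

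**What two visit columns can yield.** The statistic set (Protocol 5.3, SAP 8.3) is n, mean, median, SD, minimum and maximum.

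- Mean change: recoverable as the difference of the two visit means, but only if the same subjects are in both columns. Anyone without final spirometry breaks this.
- SD of change: √(s₁² + s₂² − 2·r·s₁·s₂). The table gives s₁ and s₂ but not the within-subject correlation r, so this is not recoverable.
- Median, minimum and maximum of change, and the number beyond −20%: not recoverable.

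**Effect of one faller on the visit mean.** Arm size is 10 (synopsis). One subject goes from 100% to 79% predicted and the others are unchanged:

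- shift in the arm mean = 21/10 = 2.1 points;
- standard error of a visit mean = SD/√10. The between-subject SD is assumed: SD 10 gives 3.2, SD 15 gives 4.7 and SD 18 gives 5.7 points.

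The shift is smaller than the standard error throughout that range.

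**Does pairing the mean help?** Assume SD 15 at both visits and r of 0.90 to 0.95.

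- SD of change = 15·√(2(1 − r)) = 6.7 (r = 0.90) or 4.7 (r = 0.95).
- Standard error of the mean change = 2.1 or 1.5.
- 95% half-width at n = 10 (t = 2.262) = about 4.8 or 3.4 points.

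Pairing is two to three times more precise, but the mean change is still only −2.1. An interval for the mean would not single out this subject either.

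**What does reveal the subject.** Arms of 10 were simulated (20,000 per setting) under assumed values: baseline mean 95% predicted, between-subject SD 10 to 15, random within-subject change with SD 3 to 5 points, and one subject falling by 21% of baseline.

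| Quantity | Result across settings |
|---|---|
| Shift in arm mean | about −2.0 points |
| Arm minimum falls by less than 10 points between visits | 66% to 80% of arms |
| Minimum of the within-subject change is −15% or lower | 87% to 97% of arms |

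The visit minimum often fails because the faller need not have started near the bottom of the arm.

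**How likely is there to be such a subject?** Among the 20 Afrezza subjects, the chance of at least one is 1 − (1 − p)²⁰: 18%, 64% or 88% for an assumed true rate p of 1%, 5% or 10%.

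**The case against.** A reader might infer that FEV1 will not be analysed, or that an individual fall would never come to light. The documents do not support either reading.

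- Protocol 5.15 does plan an FEV1 table and graph, and SAP silence does not cancel them. Both documents also promise summary tables of safety variables in general terms.
- Both documents plan subject-level listings ordered by arm, subject, visit and time. With 25 subjects and two scheduled values each, a 21% fall can be worked out by eye.
- A >20% decline is an AESI, to be reported to the sponsor within 24 hours (4.1.3), and its incidence is an endpoint.

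These points stand, and they limit the consequence. They do not supply the summary. A listing leaves the pairing to the reader. The graph helps only if drawn by subject. The AESI route depends on site staff recognising the decline and completing an AE form (4.2.2), and its definition also counts respiratory symptoms. Neither 5.15 nor SAP 8.2.4 plans a separate AESI table.

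It is also tempting to say that the endpoint (FEV1) and the criterion (percent predicted) are on conflicting scales. Over 90 days an adult's reference value should hardly change, so a relative fall in one is practically the same relative fall in the other.

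HbA1c, the primary endpoint, is likewise defined as change but summarised by visit, so the drafting habit is not specific to FEV1. FEV1 is nevertheless the one that drops out of the SAP. SAP section 2 refers to primary and secondary endpoints, but that does not explain the omission: 8.2.4 covers treatment-emergent AEs, which are not in the secondary objectives either.

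Finally, the SAP cites protocol 1.1 and was signed in March 2022, whereas version 2.0 (June 2022) added the definition of clinically relevant decline. That may explain the missing count. Whether it explains the missing endpoint cannot be checked, because version 1.1 is not available here.

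**Conclusion.** The point holds as a gap in the specified analysis of a named safety endpoint. As written, the summary tables omit the distribution of within-subject FEV1 change and the number of subjects crossing the protocol's own threshold. A single 21-point faller would move a 10-subject arm mean by 2.1 points, below the standard error of a visit mean for any assumed SD from 10 to 18. The 2.1 is arithmetic; the SDs, correlations and simulation settings are assumptions. The conclusion does not depend on them, because the missing quantities cannot be derived from visit columns whatever their values.

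The gap does not mean that a fall would go undetected: listings, AESI reports and possibly the graph remain. It should be corrected, but it does not threaten the study's conduct.

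**What to change.** In Protocol 5.15 and SAP 8.2.4:

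1. Tabulate by arm the within-subject change in FEV1 from screening to V14 or ET, in litres and percent predicted, with n, mean, median, SD, minimum and maximum, in subjects with both values. State how many lack a final value.
2. Add the number and percentage per arm with a >20% decline from baseline percent predicted, computed from the spirometry data and not from AE reports. State how the percentage is calculated and how percent predicted is obtained.
3. Draw the planned FEV1 graph with one line per subject.

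The minimum change and the count do most of the work. A confidence interval for the mean change is optional in a study that plans no inference.

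The cost is wording in two sections and one extra table. FEV1 is already scheduled in all arms at V1, V14 and ET, and no visit or test is added. The SAP needs updating from protocol 1.1 to 2.0 in any case.

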#### 6 STUDY MANAGEMENT

#### 6.1 Ethics and Consent

### 6.1.1 Regulations and Guidelines

The study will be performed in accordance with this protocol state and federal laws, and ICH guidelines for Good Clinical Practice.

### 6.1.2 Institutional Review Board

The clinical trial documents, including this protocol, will be reviewed by the relevant IRB before the start of the study.

Conduct of the trial must be approved by an appropriately constituted IRB. Approval is required for the study protocol, protocol amendment(s), ICF(s), subject information sheets, and any advertising materials. No investigational product will be shipped to a site until written IRB authorization has been received by the Sponsor or its representative.

#### 6.1.3 Informed Consent

For each trial subject, written consent will be obtained before any protocol-related activities are performed. As part of this procedure, the Investigator or a designated representative must explain orally and in writing the nature, duration, and purpose of the study, and the action of the study drug in such a manner that the subject is aware of the potential risks, inconveniences, or adverse effects that may occur. Subjects should be informed that they may withdraw from the study at any time without any resulting disadvantage. They will receive all information that is required by local regulations and ICH guidelines.

All subjects will be insured against injury caused by their participation in the study according to legal requirements. They will be informed about the insurance and the resulting obligations on their part.

## 6.1.4 Data Protection

The Sponsor will ensure the confidentiality of a subject's medical information in accordance with all applicable laws and regulations.

Personal data generated within the scope of this study must be available for inspection upon request by representatives of the Sponsors' monitors, representatives, and collaborators.

## 6.1.5 Discontinuation of the Study by the Sponsor

The Sponsor reserves the right to discontinue the study at this site or at all sites for safety or administrative reasons at any time. In particular, a site that does not recruit at a reasonable rate may be discontinued. Should the study be terminated and/or the site closed for whatever reason, all documentation pertaining to the study and study drug must be returned to the Sponsor or its representative.

The study may also be discontinued at the discretion of the Sponsor if:

Confidential Page 65 of 70

mannkind

• Two subjects in the Afrezza+AID group and two subjects in the Afrezza+degludec group are discontinued from the study due to DKA

OR

• Two subjects in the Afrezza+AID group and two subjects in the Afrezza+degludec group are discontinued from the study due to severe hypoglycemia

